12. Publication	11
13. References	11
14. Attachments	12

LIST OF ABBREVIATIONS AND RELEVANT DEFINITIONS*

CTA	Clinical Trial Agreement
De novo biobank	The information of a new data, human material or imaging collection
DMP	Data Management Plan
DPIA	Data Protection Impact Assessment
DTA	Data Transfer Agreement
EAU	European Association for Urology
Exception consent	Form Care for data Template , in Dutch: Formulier uitzondering toestemming
FSFI-6	Female Sexual Function Index – 6
GCP	Good Clinical Practice
GDPR	General Data Protection Regulation in Dutch: Algemene Verordening Gegevensbescherming
IC	Informed Consent
IFSBH	International Federation for Spina Bifida and Hydrocephalus
IFU	Instruction For Use
IIEF-5	International Index of Erectile Function – 5
MTA	Material Transfer Agreement
NWTC	Non-WMO Review Committee; in Dutch: Niet WMO Toetsingscommissie
QUALAS	QUALity of Life Assessment in patients with Spina bifida
UAVG	Dutch Act on Implementation of the General Data Protection Regulation; in Dutch: Uitvoeringswet Algemene Verordening Gegevensbescherming
WMO	Medical Research Involving Human Subjects Act, in Dutch: Wet Medisch-wetenschappelijk Onderzoek met Mensen

**Please delete abbreviations/definitions that are not applicable and add any new ones that are used in the research protocol*

PROTOCOL SUMMARY

Children with spina bifida require care from various medical and paramedical specialists throughout their life. The availability and organization of the care needed differs between the European countries. The EAU and IFSBH are both organizations with the aim to improve patient care and clinical outcomes for children with spina bifida.

We have set up a collaboration to evaluate the differences in organization of care and clinical treatment received and how this affects outcomes with regard to quality of life and sexuality.

A digital survey has been constructed which will be distributed among children and adolescents with spina bifida and their caregivers. The IFSBH and national patient organizations will send out invitations to their members. Children and adolescents from 8 – 18 years of age with spina bifida are eligible for inclusion.

The survey includes a primary survey developed in collaboration between panelmembers of the EAU pediatric urology guidelines and patient representatives. The second part includes validated questionnaires to evaluate Quality of life with the QUALAS and sexual function with the IIEF-5/FSFI-6 for boys/girls respectively.

Primary outcome will be the quality of life in children and adolescents with spina bifida. We will evaluate if their demographic differences influence the quality of life and if differences are seen between the different European countries. Secondary outcomes include differences in sexual function, organization of care, treatment received, treatment options available, with also a focus on differences between the different European countries.

The results of this survey will be evaluated and interpreted within a sounding board group consisting of children/adolescents/adults with spina bifida, patient representatives from IFSBH and panel members of the EAU Pediatric Urology guidelines panel. Finally, the interpreted results will be used to update the EAU Pediatric Urology guidelines to make these more patient centered.

There are no known risks of participating in the study given the fact that participation includes only completion of questionnaires and data about standard of care. Furthermore, the study is completely voluntary and the results will be completely anonymous.

1. Introduction and rationale

Children with spina bifida require care from various medical and paramedical specialists throughout their life. The availability and organization of the care needed differs between the European countries. It can be expected that this variety results in differences in outcome of care.

Children with spina bifida have stated that for future research they feel it is important that quality of life and sexuality are investigated. [1]

The EAU Pediatric Urology guidelines panel wants to ensure that patients with spina bifida receive the best possible care based on the best available clinical evidence. [2] Additionally, we want to improve the clinical guidelines by including patients perspectives. The IFSBH represents patients with spina bifida and values the promotion and protection of the human rights of patients with spina bifida thereby improving quality of life.

Together with the IFSBH we have set up a collaboration to investigate how we can make the guidelines more patient centered and thereby improve quality of care and quality of life.

For this aim we have developed a survey to evaluate the current organization of care, demographic features and received treatment. The outcome of this survey will show the exact differences in care between European countries. We have included two validated questionnaires to measure the effect this has on quality of life and sexuality. The information gathered will be used to adapt the clinical EAU Pediatric Urology guidelines.

2. Objective(s)

The main objective is to improve the quality of life of patients with spina bifida by updating the guidelines according to the differences found in care and how this impacts patients outcomes. We will evaluate the difference in organization of care between different European countries based on the outcomes of the primary survey. The baseline quality of life and sexuality reported will be evaluated with the QUALAS and the IIEF-5/FSFI-6 questionnaires [3-6]. We will then explore the relationship between how care is organized and how this affects quality of life and sexuality. The results of this study will be used to update the EAU Pediatric Urology clinical guidelines. Also, it will highlight the direction for future research to improve patients care and thereby quality of life and/or sexuality, which patients with spina bifida have stated they themselves find important.

3. Study type

3.1 Study type:

- Retrospective
- Prospective
- Combination Retrospective/Prospective

3.2 Check all the applicable boxes:

- Medical records (re-use of data from healthcare, including AI)
- Case report
- Re-use data from research
- Evaluations of quality of healthcare (retrospective)

QoL in patients with spina bifida

- Research with additional use of residual material from regular healthcare
- Research with re-use of human materials from research or existing biobank
- Research with human materials without biobank
- De novo biobank (human material obtained without burdensome or invasive procedures)
- Post marketing survey research with medical devices
- Phase IV research
- Healthcare evaluation research (prospective)
- Medical devices
- In Vitro Diagnostic Tests
- Other research, *describe*

4. Study population

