4.4 Sample size calculation

Since this is a descriptive study no minimal sample size is required.

However, our aim is to include 500 patients.

4.5 (Planned) start date

Depending on the approval of the NWTC.

Start date 01.01.2023.

4.6 (Planned) end date

The digital questionnaire will be available for 3 months.

5 Methods

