5.1 A digital survey has been created on Surveymonkey: <https://www.surveymonkey.com/r/7WSB9S9>

This digital survey includes a primary survey regarding basic demographic features, medical treatment and organization of care. This survey was constructed by the EAU guidelines panel and the IFSBH patient representatives. The second part of the digital survey includes two validated questionnaires. The QUALAS is a validated questionnaire regarding quality of life in patients with spina bifida. There are two different versions for the ages 8-12 and 13-18 years. To evaluate sexuality the IIEF-5 (for boys) and the FSFI-6 (for girls) are used. These questionnaires are validated and are used in patients with spina bifida to evaluate sexual function as standard of care. Only children aged 13 years or older will be asked if they want to answer questions about sexuality and if they answer yes they will be asked for which gender they want to answer questions about their sexuality. After this they'll get the IIEF-5 or FSFI-6 questionnaire.

This digital survey is available in nine languages: English, Spanish, German, Italian, French, Danish, Greek, Turkish and Dutch.

The link to surveymonkey will be distributed by the IFSBH and local patient organizations among their members.

After the data have been collected, the general results of the survey will be evaluated and interpreted with a sounding board group. When patients participate with the digital survey they will not be involved in the sounding group. This sounding board group will consist of children/adolescents/adults with spina bifida who are representatives from the patient organization IFSBH and panel members of the EAU. This sounding board group will meet for a day. Finally, the results will be used to update the EAU Pediatric Urology guidelines.

5.2 This is a demographic study. Patients will not receive any difference in treatment.

5.3 The survey only has to be completed once and is completely voluntary. The questionnaire will take around 15 minutes to complete. It will not influence their own treatment.

5.4 There are no known risks of participating in the study given the fact that involves only the completion of questionnaires and data about standard of care. Also, all responses will be anonymous and completely voluntary. No personal identifying information will be used when reporting the data.

6 Unexpected discoveries

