6.1 Is there a chance of unexpected discoveries?

Yes

No

7 Exchange, sharing or transfer of data and/or human material and/or images outside Erasmus MC

The data will be collected and stored within the Erasmus MC in the Castor program. Only anonymous data will be collected and shared with collaborating colleagues from the EAU Pediatric Urology guidelines panel from their respective institutions outside the Erasmus MC. The institutions are:

- University of Leuven, Leuven, Belgium

- Medical University of Innsbruck, Innsbruck, Austria
- Hacettepe University, Ankara, Turkey
- University Medical Center Groningen, Rijks University Groningen, Groningen, The Netherlands
- Istanbul Biruni University, Istanbul, Turkey
- East of England Deanery, Urology, Cambridge, United Kingdom
- University of Medical Center Mannheim, Heidelberg University, Mannheim, Germany
- Aarhus University, Aarhus, Denmark
- Fondazione IRCCS Ca' Granda, Ospedale Maggiore Policlinico, Milan, Italy
- Pediatric Hospital Bambin-Gesù, Rome, Italy
- Radboud University Medical Center, Nijmegen, The Netherlands
- University of Zurich, Zurich, Switzerland
- Beacon Hospital, Dublin, Ireland

8 Statistical analysis

8.1 Main study parameter/endpoint:

The primary parameter is to evaluate quality of life in children with spina bifida using the QUALAS questionnaire. We will evaluate the differences in quality of life between European countries. Also, we will evaluate which demographic parameters are of influence on quality of life.
Descriptive statistics will be used.

8.2 Secondary study parameters/endpoints:

Secondary parameters will include sexual function using the outcomes of the IIEF-5/FSFI-6 questionnaires, also in relation to differences between European countries. Other parameters include organization of care, treatment received, treatment options available, which will all be extracted from the primary survey. Again descriptive statistics will be used.

9. Recruitment and consent

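### The primary comparison of quality of life between countries is descriptive only, yet its results are committed to a guideline update, and nothing in the plan separates real country differences from sampling variation

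*Combined protocol and SAP*

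**What the plan says.** Section 2 states the main objective as improving quality of life "by updating the guidelines according to the differences found in care and how this impacts patients outcomes". The same section adds: "The results of this study will be used to update the EAU Pediatric Urology clinical guidelines". Section 5.1 ends its account of the procedure in the same way: "Finally, the results will be used to update the EAU Pediatric Urology guidelines". Section 1 makes the same commitment in slightly different words. None of these statements carries a condition.

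Section 8.1 places the country comparison within the primary parameter: "We will evaluate the differences in quality of life between European countries". The whole of the method given is "Descriptive statistics will be used". No interval, model, test, adjustment for many comparisons, relevant difference or minimum number per country is given.

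Section 4.4 waives a sample size calculation because the study is descriptive, and then says: "However, our aim is to include 500 patients".

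There is a step between results and guideline. The Protocol Summary says "The results of this survey will be evaluated and interpreted within a sounding board group", and continues: "Finally, the interpreted results will be used to update the EAU Pediatric Urology guidelines to make these more patient centered". Section 5.1 repeats the sounding board step. Neither place gives the group a criterion for judging whether a country difference is real.

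**The concern.** Country means from a finite survey always differ. When many countries are compared, the distance from highest to lowest can look substantial even if quality of life is the same everywhere. A table of bare means gives the reader no way to see this.

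The table is meant to be used. The plan intends to relate how care is organised to quality of life and to carry the results into a clinical guideline. If a country ranks high by chance, the features of its care may be read as the reason and reach the sounding board as a lead. The plan names no outcome of the analysis that would be reported as a country difference not shown. Recruitment by open distribution through patient organisations also makes some small national samples likely, and small samples produce the most extreme means.

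**Working it through.** **The plan's own figure.** The target of 500 has no effect size, SD, precision or power behind it, so there is nothing to reproduce.

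**Inputs**
- Total N = 500 (Section 4.4).
- Number of countries k: not stated. The 13 data-sharing institutions in Section 7 lie in 10 countries, and Section 4.2 lists nine languages, but neither list defines the recruiting countries. Assumption: k = 10, with 5, 8 and 13 as alternatives.
- SD of a QUALAS score: not stated. Results are in SD units (SD = 1).
- Country sizes: not stated. Base case equal, n = 500/k.
- True country difference: none.

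**Step 1: gap between the highest and lowest country mean.** Each mean has standard error 1/√n. For k = 10, n = 50 and the standard error is 1/√50 = 0.141. The expected range of 10 independent standard normal values is about 3.08, so the expected gap is 3.08 × 0.141 ≈ 0.44 SD. The probabilities of exceeding a given gap come from simulating sets of country means.

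**Step 2: at least one unadjusted pair excludes zero.** With 10 countries there are 10 × 9/2 = 45 pairs. With equal sizes, some pairwise 95% interval excludes zero when the range exceeds 1.96 × √(2/n). For n = 50 this is 1.96 × 0.2 = 0.392 SD. The probability is the studentized range tail at 1.96 × √2 = 2.77 with k groups and 500 − k degrees of freedom.

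| Countries | n each | Expected gap (SD) | Gap > 0.3 SD | Any unadjusted pair |
|---|---|---|---|---|
| 5 | 100 | 0.23 | 21% | 29% |
| 8 | 62.5 | 0.36 | 70% | 51% |
| 10 | 50 | 0.44 | 89% | 63% |
| 13 | 38.5 | 0.54 | 99% | 76% |

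For 10 countries, other cut-offs give 99% above 0.2 SD, 60% above 0.4 SD, 27% above 0.5 SD and 8% above 0.6 SD.

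**Step 3: uneven sizes.** With 10 countries of 120, 90, 70, 60, 50, 40, 30, 20, 12 and 8 (sum 500), a gap above 0.3 SD appears in 97% of surveys and at least one unadjusted pair excludes zero in 60%.

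**Step 4: what a controlled comparison requires.** With 10 countries of 50, a Tukey-adjusted contrast needs a gap of about 0.64 SD. That exceeds the 0.44 SD expected by chance, and chance reaches it in 5% of surveys by construction.

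**Step 5: what such control costs.** For an overall test of country with between-country SD τ, power is P(F > Fcrit/(1 + nτ²)).
- 10 countries of 50, τ = 0.2: Fcrit = 1.90, 1 + 50 × 0.04 = 3, 1.90/3 = 0.63, power 77%.
- Equal sizes with 5 to 13 countries, τ = 0.2: 75–77%. At τ = 0.3: 92–96%.
- The uneven sizes of Step 3, τ = 0.2: about 73%.
- One QUALAS age version alone, 10 countries of 25, τ = 0.2: Fcrit = 1.92, 1 + 25 × 0.04 = 2, 1.92/2 = 0.96, power 47%.

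**The case against.** The strongest reply is that this is a descriptive survey and claims no more. The plan has no decision rule, test or threshold, so it has no false-positive rate to criticise. The sentence in Section 2 concerns differences in care and their impact on outcomes, not quality-of-life differences between countries alone. The sounding board interprets the results before they are used. The update also has a second purpose, making the guideline more patient centred, which could justify changes even if quality of life were the same in every country.

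Much of this stands. A reader might infer that the guideline update is set off automatically, and almost always, by chance country gaps. The documents do not support that. No trigger is written down, the number of countries is an assumption, and any rate depends on what is taken as a difference. With 10 equal countries it runs from 99% for a gap above 0.2 SD down to 27% for one above 0.5 SD.

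The reply does not remove the narrower point. Section 8.1 does plan a country comparison as part of the primary parameter, and Section 2 does intend to relate care to quality of life. A sounding board given bare means and no criterion cannot tell noise from signal, however expert its members.

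A further fair objection is directed at one possible remedy. Allowing guideline use only after a significant test of country would be wrong. Such a test does not examine the link between care and outcome, which may exist within countries without any country effect, and its power is modest. That objection is accepted.

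**Conclusion.** The concern holds in this limited form: a primary comparison between countries feeds a guideline update without condition, and the planned analysis has no means of separating real variation from sampling variation. With 500 responses in 10 equal countries and no true difference, the average gap between extremes is 0.44 SD. At least one unadjusted pair would stand out in 63% of surveys (29% with 5 countries, 76% with 13).

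These figures rest on an assumed number of countries, equal sizes unless stated, and one score in SD units. They show how easily chance gaps could be misread. They are not the error rate of a rule in the plan, and they do not show that the guideline would be changed wrongly. The correction is inexpensive and should be made before the data are analysed.

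**What to change.** **Section 8.1.** For each QUALAS version, fit one model with a random country effect. Report the between-country SD with its 95% CI. Present countries as shrunken estimates with intervals, or as Tukey-adjusted contrasts, and not as raw means or selected pairs.

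**Sections 2 and 5.1.** State that these estimates go to the sounding board together with their uncertainty. State also that country gaps compatible with chance are reported as no reliable difference shown, without claiming that countries are equal, and are used only to point to further research, a use that Section 2 already provides for.

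**What not to add.** Do not make the guideline update, or the analysis of care against outcome, conditional on an F test of country. Descriptive findings on care and on patients' views can still inform the guideline.

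**Cost.** A few sentences of protocol text and one model per QUALAS version on data already being collected. The downside is that modest true differences will often be reported as not shown. At a between-country SD of 0.2, an overall test has about 72–77% power with the age versions pooled, and about 47% per version with 25 children per country. The protocol should state this limit openly.

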4.1 Population (base)

Children with spina bifida aged between 8 and 18 years old.

4.2 Inclusion criteria

In order to be eligible to participate in this study, a subject must meet all of the following criteria:

- Must have spina bifida
- Must be able to complete the digital survey, with help of caregivers allowed.
- Speak one of the nine available languages:
 - o English,
 - o Spanish,
 - o German,
 - o Italian,
 - o French,
 - o Danish,
 - o Greek,
 - o Turkish,
 - o Dutch

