4.3 Exclusion criteria

A potential subject who meets any of the following criteria will be excluded from participation in this study:

- Aged over 18 years or under 8 years of age
- Does not have spina bifida

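### Does the absence of a country criterion let children treated outside Europe distort results meant for a European guideline?

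*Combined protocol and SAP*

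**What the plan says.** Section 4.1 gives the base population as "Children with spina bifida aged between 8 and 18 years old". Section 4.2 begins "In order to be eligible to participate in this study, a subject must meet all of the following criteria"; the items are spina bifida, ability to complete the digital survey (with help allowed) and "Speak one of the nine available languages". Section 4.3 excludes on two grounds only: "Aged over 18 years or under 8 years of age", and not having the diagnosis. The Protocol summary is equally silent on geography: those in the age range "years of age with spina bifida are eligible for inclusion".

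On recruitment, the Protocol summary states "The IFSBH and national patient organizations will send out invitations to their members". The abbreviation list expands IFSBH as "International Federation for Spina Bifida and Hydrocephalus".

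On analysis, the Protocol summary says "We will evaluate if their demographic differences influence the quality of life and if differences are seen between the different European countries". Section 8.1 has three parts: quality of life by QUALAS in children with spina bifida, its differences between European countries, and the demographic parameters that influence it. Section 8.2 applies the European comparison to sexual function. All of it is descriptive. The results are to inform the EAU Pediatric Urology guideline.

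**The concern.** The rationale, the comparison of care organisation and the guideline are European, but nobody is kept out on grounds of country. The survey link goes out through a federation with an international name, and English, Spanish and French are spoken well beyond Europe. A child living and treated elsewhere can therefore meet every criterion.

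That child's answers could enter the overall QUALAS description, the demographic analysis and the exploration of how care organisation relates to quality of life and sexuality. The last would matter most, because care organisation is what the protocol expects to differ between health systems. The plan does not define the European countries or say whether Turkey is one of them, though Turkish is a survey language. Responses are anonymous, so if country were not asked, out-of-area answers could not be found later. Readers would then not know which population the overall results describe.

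**Working it through.** **Eligibility.** Sections 4.1, 4.2, 4.3 and the Protocol summary contain no country criterion. Language is not a substitute for one. This part of the concern is correct.

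**Which analyses could be affected.**

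- *Quality of life and sexual function by country (8.1, 8.2), and care organisation by country (section 2).* Each is worded as between European countries. A response from elsewhere has no place in them.
- *Care organisation in relation to outcomes.* The sentence in section 2 carries no geographic limit when read alone. The end of section 1 does supply one: the survey is to show how care differs between European countries, and the questionnaires are there to measure what those differences do to quality of life and sexuality.
- *Overall QUALAS description and demographic influences (8.1).* These carry no geographic limit. Describing all eligible respondents is what 8.1 literally says, so including a child from elsewhere breaks no stated rule. A European target for these results is an inference from the aims.

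**Is country recorded?** The questionnaire is an attachment that is not reproduced. However, the comparison between countries is part of the primary analysis, and it cannot be done without country. The reasonable reading is that country is asked, and out-of-area responses can then be identified and separated.

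**How large could the effect be?** The documents give neither a non-European share nor a QUALAS SD, so p and d below are assumptions. Let p be the share of respondents from outside Europe, and d the difference of their mean from the European mean m, in SD units.

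Overall mean = (1 − p) × m + p × (m + d) = m + p × d, so the shift is p × d.

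| p | children out of 500 | shift at d = 0.2 | shift at d = 0.5 |
|---|---|---|---|
| 0% | 0 | 0 | 0 |
| 5% | 25 | 0.010 SD | 0.025 SD |
| 10% | 50 | 0.02 SD | 0.05 SD |
| 20% | 100 | 0.04 SD | 0.10 SD |
| 30% | 150 | 0.06 SD | 0.15 SD |

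For scale, the 95% half-width of a mean at the target of 500 (section 4.4) is 1.96/√500 = 0.088 SD. The shift reaches that size only when p = 0.088/d, which is about 18% at d = 0.5 and 44% at d = 0.2.

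**Precision.** Section 4.6 closes the survey after 3 months, not at a count. The number of European responses is therefore the same with or without a country criterion, and a criterion would gain no precision.

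**The case for a change.** The strongest reply is that a descriptive study delivers a description of a defined population, so an undefined population touches its main output. A shift in the mean is bias, and more respondents do not shrink it. With a share of 30% and a difference of 0.5 SD it would be 0.15 SD, more than the sampling error. The effect on associations cannot be computed from the documents at all. And if the list of European countries is drawn up after responses are seen, Turkey could be counted in or out with knowledge of the data.

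Some of this stands. The plan lists no countries, and comparing bias with a half-width gives only a sense of scale. But nothing in the documents supports a share of 30%, or any share above zero: the only sign of reach beyond Europe is one word in the federation's name. No passage says that non-European members will be invited. On Turkey, section 7 names two Turkish institutions, in Ankara and Istanbul, among the collaborating guideline-panel sites. With Turkish as a survey language, this points to Turkey being within the study's area, though it is not a formal definition. No hypothesis test or decision threshold hangs on the overall mean, so a later choice about one country has limited room to mislead, and showing results by country makes it visible.

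**Conclusion.** The text is as described: eligibility has no country limit and section 8 has no European analysis set. It does not amount to a fault that requires a change. The European comparisons exclude other responses by their wording, the link between care and outcomes is tied to European differences in section 1, and the overall description in 8.1 claims no European limit. A new eligibility criterion would turn children away from a short, voluntary survey without adding a single European response.

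The size is somewhere from zero, if nobody outside Europe responds, to 0.10 SD in the overall mean at an assumed share of 20% and difference of 0.5 SD. The documents do not say where in that range the study falls. The conclusion rests mainly on country being recorded, which the planned country comparison requires but which the unseen questionnaire cannot confirm. Given that, stating which countries are counted as European and showing any other responses separately is ordinary analysis and reporting practice.

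### One entry criterion covers both the care items and the self-report questionnaires, and the plan does not say whether a caregiver may answer alone

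*Combined protocol and SAP*

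**What the plan says.** All places are in the combined protocol and SAP.

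- **Entry (4.2).** To be eligible, "a subject must meet all of the following criteria", one of which is "Must be able to complete the digital survey, with help of caregivers allowed". The subject is the child; the caregiver appears only as a helper.
- **What the survey contains (5.1).** "This digital survey includes a primary survey regarding basic demographic features, medical treatment and organization of care". Then: "The second part of the digital survey includes two validated questionnaires", namely QUALAS and IIEF-5 or FSFI-6. The sexuality part is optional: "Only children aged 13 years or older will be asked if they want to answer questions about sexuality".
- **Endpoints (8.1, 8.2).** Quality of life by QUALAS is primary. For the care and treatment endpoints: "Other parameters include organization of care, treatment received, treatment options available, which will all be extracted from the primary survey".
- **Population (4.1).** "Children with spina bifida aged between 8 and 18 years old", with no limit by ability. The exclusion criteria in 4.3 concern only age and absence of spina bifida.
- **Recipients (Protocol summary).** The survey is to be "distributed among children and adolescents with spina bifida and their caregivers".
- **Use of results (section 1).** The survey is expected to show precisely how care differs between countries and to feed into the guidelines. No restriction to children able to respond is attached.

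The text does not define help, describe a caregiver-only route, provide for recording who answered, or plan to count children who could not take part. The opening agreement question in 9.1 is put to patients.

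**The concern.** The two parts of the survey need different informants. Which treatments a child has had and how care is organised are facts that a caregiver can report. Quality of life and sexual function concern the child's own experience. (That distinction is mine; section 5.1 does not say who must answer which part.) A single criterion based on the child's ability to respond therefore fits the second part better than the first.

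Because help is undefined, there are two risks. If the criterion is applied strictly, some children are left out of the care description for a reason unrelated to whether their care can be described, while guidelines based on the results would apply to them too. If it is applied loosely, caregivers supply QUALAS answers that cannot later be told apart from children's own. Families reached through different patient organisations and in nine languages may also differ in how they understand the rule.

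**Working it through.** **Step 1: is there a figure to reproduce?** No. The 500 patients in 4.4 are an aim without a derivation, and no rate of inability to respond is given. The check is a reading of the text followed by illustrative arithmetic.

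**Step 2: the text side by side.** 4.2 applies one criterion to each subject. 5.1 makes the survey in that criterion the sum of two parts. 8.2 takes the care endpoints from the first part only, and 8.1 takes the primary outcome from the second. So one rule governs both sets of endpoints, with no separate rule for either. 4.1 and section 1 describe the population and the care conclusions without reference to ability.

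**Step 3: strict reading, one country.** Inputs, all assumed:

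- f = share of children unable to respond even with help
- d = care rate in those children minus the rate in the others, in percentage points

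True proportion = (1 − f) × rate in included + f × rate in excluded = rate in included + f × d. The survey shows the rate in the included, so it is off by f × d:

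| f | d = 10 | d = 20 | d = 40 |
|---|---|---|---|
| 5% | 0.5 | 1.0 | 2.0 |
| 10% | 1.0 | 2.0 | 4.0 |
| 20% | 2.0 | 4.0 | 8.0 |
| 30% | 3.0 | 6.0 | 12.0 |

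Example: with 50% in the included, 80% in the excluded and f = 15%, the true figure is 0.85 × 50 + 0.15 × 80 = 54.5%, and the survey shows 50%.

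**Step 4: strict reading, two countries.** With the same d in both, the contrast is off by (fA − fB) × d. In absolute size, for d = 10, 20 and 40:

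- f = 10% in both: 0, 0, 0 points
- f = 5% and 15%: 1, 2, 4 points
- f = 5% and 25%: 2, 4, 8 points

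Example with the 50% and 80% above: f = 5% gives 0.95 × 50 + 0.05 × 80 = 51.5%, and f = 25% gives 0.75 × 50 + 0.25 × 80 = 57.5%. The survey shows 50% in both and misses a difference of 6.0 points. If f and d are equal in the two countries, the contrast is unaffected.

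**Step 5: scale.** With all 500 patients, the 95% half-width for a proportion of 50% is 1.96 × √(0.25/500) = 4.4 points. Sampling error shrinks with more respondents; the shift in step 3 does not.

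**Step 6: loose reading.** If a share q of QUALAS records is answered by caregivers alone, the overall mean differs from the self-report mean by q × (mean proxy score − mean self-report score). The documents give none of these quantities. Without a record of who answered, q could not be estimated from the data either.

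**The case against.** The strongest reply is that the criterion is softer than it looks. Help is expressly allowed without a limit, the survey goes to caregivers as well, and the link is sent out with no ability check described, so a caregiver may well enter the answers. Section 4.1 is headed as the base population, and 4.2 narrows it in the open; that is ordinary generalisability. One sample for both parts is also defensible, because section 2 sets out to relate care to quality of life, and records without QUALAS cannot serve that aim. The questionnaires are listed among the attachments but are not reproduced, so an item on who answered may already exist. Finally, the numbers are assumed, and precision is limited: with 50 children in each of two countries (assuming ten equal countries from 500), the 95% half-width for a difference near 50% is 1.96 × √(2 × 0.25/50) = 19.6 points, well above a 6-point shift.

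Much of this stands. The extent of any exclusion is not shown, and for a single pair of small countries the shift would be lost in sampling error. But the reply relies on the loose reading, which brings unflagged proxy answers into QUALAS. Under either reading the protocol text does not let an analyst say whom the figures describe.

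A reader might also infer that a child must be able to complete every item. The criterion does not say so, and the sexuality questionnaires are opt-in from age 13.

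**Conclusion.** The point holds as an ambiguity with two unwelcome outcomes. Strictly read, children who cannot answer even with help may be missing from the care and treatment description. Loosely read, proxy and self-report may be mixed in the primary outcome without a flag. It is worth correcting but does not undermine the study.

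The size is unknown. The range of 0.5 to 12 points for one country's proportion rests wholly on assumed shares (5% to 30%) and assumed care differences (10 to 40 points). The direction also depends on whether the children left out receive more or less of a given treatment.

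Two stronger conclusions might be drawn, and the documents support neither. The first is that the most impaired children do drop out. This is plausible, but nothing in the text states it, and the allowance for help works against it. The second is that the comparison between countries is biased. That requires the share left out, or how their care differs, to vary by country. Otherwise the consequence is that each country's figure does not represent all children with spina bifida in the 8 to 18 age range.

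**What to change.** 1. **Section 4.2:** split the criterion. The primary survey may be answered by the child or by a caregiver alone. QUALAS and IIEF-5/FSFI-6 are answered only by a child able to answer, with help allowed. State what counts as help, as distinct from answering in the child's place.
2. **Section 5.1:** add one item recording who answers (child, child with help, caregiver alone). The caregiver-alone option skips the questionnaires. The survey already branches by age and by choice, so the mechanism exists. If the attached questionnaires already contain such an item, describe it in the protocol and use it for the routing.
3. **Section 9.1:** adapt the opening agreement question for caregiver-alone records.
4. **Section 8.1:** state that quality of life refers to children able to report, and give by country the number routed past QUALAS.

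The cost is one extra item in nine languages, adapted agreement wording, and some records with care data but no QUALAS that must be counted separately. After a favourable opinion, the change has to go to the review committee under section 11. It belongs before the three-month window opens: responses are anonymous, so who answered cannot be established afterwards by contacting respondents.
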